### 2.9 Treatment for Non-Compliance

For the primary endpoint, and for secondary end points that are significantly affected by treatment assignment we will estimate the causal effect of the actual treatment given using an instrumental variable approach [7].

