## 2 TRIAL SUMMARY

**Title:** Reevaluation Of Systemic Early neuromuscular blockade (ROSE)

**Objective:** To assess the efficacy and safety of early neuromuscular blockade in reducing mortality and morbidity in patients with moderate-severe ARDS in comparison to a control group with no routine early neuromuscular blockade.

**Hypothesis:** Early neuromuscular blockade will improve mortality prior to discharge home before day 90, in patients with moderate-severe ARDS.

**Study Design:** Multi-center, prospective, 2-arm, unblinded, randomized clinical trial of two management strategies of neuromuscular blockade (also called skeletal muscle relaxant and muscle relaxant).

1. We will emphasize early screening and protocol initiation, and enroll a maximum of 1408 patients with a confirmed and established PaO2/FiO2 < 150.
  - ✓ We will allow determination of PaO2/FiO2 inclusion criteria from SpO2 pulse oximetry measurement.
2. Early neuromuscular blockade group
  - ✓ Patients will receive a cisatracurium besylate bolus of 15 mg, followed by a continuous infusion of 37.5 mg/hour for 48 hours.
  - ✓ We will protocolize deep sedation to Ramsay of 5-6 (RASS of -4 to -5, or Riker of 1-2) before starting, and during, the 48 hour infusion. We do not mandate sedative type or dose.
  - ✓ We will protocolize high PEEP/FiO2 titration (based on published, safe, feasible high PEEP protocols).
3. No routine early neuromuscular blockade group (control group)
  - ✓ We will recommend non-neuromuscular blockade interventions for refractory hypoxia and that neuromuscular blockade only be used for refractory elevated plateau pressure; treating clinicians can use neuromuscular blockade if thought necessary
  - ✓ We will recommend clinicians target light sedation titrated to a Ramsay 2-3 (RASS of 0 to -1, or Riker 3-4) and/or perform daily sedation interruption. Higher doses of sedation will be allowed for respiratory distress, ventilator dyssynchrony, or hypoxia. We do not mandate sedative type or dose.
  - ✓ We will protocolize high PEEP/FiO2 titration (based on published, safe, feasible high PEEP protocols).
4. Prone positioning
  - ✓ We will recommend sites wait at least 12 hours (as per PROSEVA[1]) before proning, and to avoid automatic use of neuromuscular blockade with proning.
5. Other care

- ✓ We will protocolize low tidal volume ventilation and spontaneous breathing trials in both arms.

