### 1. Secondary Outcomes:

- ICU Acquired Weakness
- IL-6 levels (plasma)
- Hospital mortality to day 28
- Ventilator free days to day 28
- Organ failure free days to day 28
- ICU-free days at day 28
- Hospital-free days at day 28
- Physiologic measures
- Long term outcome assessments
- Use of rescue procedures
- Paralysis recall, in-hospital
- Supraventricular tachycardia and new onset atrial fibrillation

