## 1.6 Sample Size/Interim Monitoring

1. With a 35% mortality rate in the control arm and 27% mortality rate in the intervention arm, the maximum required total sample size is 1408 subjects.
2. The principal analysis will be intent-to-treat, based upon randomization assignment.
3. Trial progress will be evaluated by an independent Data and Safety Monitoring Board (DSMB) to determine if the study should stop for superiority of either Active or Control therapy. There will be two interim analyses and a final analyses conducted when approximately each successive 1/3 of the patients have been enrolled.

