## **2. Data Analysis Plan**

### 2.1 Study Population

There is only one study population. All analyses will be by intention to treat

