### 2.3 Analysis Methods for: Secondary Outcomes, Descriptive Variables, Safety Outcomes, Patient Characteristics

Continuous secondary outcomes will be compared between treatment groups using a t-test. Ordinal secondary outcomes (defined as outcomes with ordinal levels such as none, mild, moderate...) will be compared between groups using the Cochran-Mantel-Haenszel ANOVA (row mean score) test. Categorical secondary outcomes will be compared between treatment groups using a Chi-square or Fisher's exact test as appropriate to the sparseness of the data. All tests will use a two sided p=0.05 significance level. There will be no correction for multiple comparison.

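### SAP 2.9 gives the instrumental-variable estimate for a secondary endpoint only after a significant ITT test, so reported estimates are inflated on average and the wider interval is missing when ITT is null

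*SAP*

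**What the plan says.** SAP 2.9 treats the two kinds of endpoint differently. The primary endpoint gets an IV estimate in any case. For the rest, the text is: "for secondary end points that are significantly affected by treatment assignment we will estimate the causal effect of the actual treatment given". SAP 2.3 sets the threshold: "All tests will use a two sided p=0.05 significance level", and "There will be no correction for multiple comparison".

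No other section gives a non-compliance-corrected estimate. SAP 2.1 states: "There is only one study population. All analyses will be by intention to treat". SAP Appendix A2 lists blockade received, in both arms, as descriptive only.

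The protocol expects departures from assignment. Its Trial Summary says of the control group that "treating clinicians can use neuromuscular blockade if thought necessary". Section 5.1.3 lets the infusion stop before 48 hours after sustained improvement or for safety concerns.

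The list of secondary outcomes under SAP 1.5 includes ICU-acquired weakness, "Paralysis recall, in-hospital" and supraventricular tachycardia or new atrial fibrillation. SAP Appendix A1 keeps weakness as a secondary outcome but labels the other two as safety, so it is unclear whether 2.9 reaches them at all.

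**The concern.** Blockade in controls and early stopping in the active arm shrink the ITT difference relative to the effect of the drug in those who follow their assignment. SAP 2.9 exists to describe that second effect. Making it conditional on the ITT p-value has two consequences.

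- **When the condition is met**, the reported estimate comes from the part of the sampling distribution that crossed the threshold, so on average it is too far from zero. If the drug has no effect on an outcome, every interval reported under this rule excludes zero, apart from small differences between the two standard errors.
- **When the condition is not met**, the reader sees only the ITT interval. For a harm, the open question is then how large an effect of treatment received is still compatible with the data, and the IV interval, which would show this, is not produced.

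This matters most for harms. Protocol 3.1 and 3.6 give inadequate assessment of weakness, paralysis recall and post-traumatic stress in the earlier trial as reasons for doing this one.

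**Working it through.** **The plan's own figure.** The SAP contains no calculation for 2.9. To confirm the design inputs, I reproduced the sample size for "35% mortality rate in the control arm and 27% mortality rate in the intervention arm", two-sided alpha 0.05 and power 0.90:

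n per arm = [1.960·√(2·0.31·0.69) + 1.282·√(0.35·0.65 + 0.27·0.73)]² / 0.08² = 4.482 / 0.0064 = 700.3, rounded up to 701, total 1402.

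The stated maximum is 1408 with three looks, so it reproduces.

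**Assumptions.** The documents give no weakness rate, number assessable or receipt rates. I assumed:
- control-arm rate p0 of 30% or 40%;
- n = 250, 350 or 450 assessed per arm, out of 704;
- true harm in compliers of +10 points;
- difference between arms in blockade received, r, of 0.9, 0.8 or 0.7, with r = 1 as reference.

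**Formulas.** The IV (Wald) estimate is the ITT difference divided by r. It therefore carries the same relative error as the ITT estimate and, ignoring sampling error in r, the same z statistic. With d = 0.10·r, p1 = p0 + d, SE = √[p0(1−p0)/n + p1(1−p1)/n] and θ = d/SE:

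- probability that the IV estimate is produced: P = Φ(θ−1.96) + Φ(−θ−1.96)
- mean exaggeration when produced: [θP + φ(1.96−θ) − φ(1.96+θ)] / (θP)

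**Two worked cases.**
- p0 = 0.30, n = 450, r = 0.9: d = 0.09, SE = 0.0315, θ = 2.85, P = 0.81, exaggeration 1.12.
- p0 = 0.40, n = 250, r = 0.7: d = 0.07, SE = 0.0442, θ = 1.58, P = 0.35, exaggeration 1.66.

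**All cases (range over p0 and n).**

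| Receipt difference r | IV estimate produced | Mean exaggeration when produced |
|---|---|---|
| 1.0 | 62% to 88% | 1.07 to 1.27 |
| 0.9 | 53% to 81% | 1.12 to 1.37 |
| 0.8 | 44% to 72% | 1.18 to 1.50 |
| 0.7 | 35% to 61% | 1.28 to 1.66 |

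The more non-compliance there is, the less often the correction is produced and the more it exaggerates when it is. Exaggeration depends on the power of the ITT test: 1.41 at 50% power, 1.13 at 80%, 1.06 at 90%.

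**Second set of assumptions, by simulation (40,000 trials each).** Base rate 30%, 8-point harm in compliers:
- 900 assessed in total: produced in 72% of trials with full compliance (exaggeration 1.18), falling to 33% when 90% of active and 30% of control patients receive blockade (1.73).
- All 1408 assessed: 89% falling to 47%, exaggeration 1.07 rising to 1.44.
- Without the condition, the mean IV estimate is 0.080 to 0.081 against a true 0.08.

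**What is omitted when ITT is null.** Assume 350 per arm, 35% vs 41%:
- ITT: SE = √(0.35·0.65/350 + 0.41·0.59/350) = 0.0366; difference +6.0 points, 95% CI −1.2 to +13.2. Not significant, so 2.9 produces nothing.
- IV at r = 0.7: 6.0/0.7 = +8.6 points, 95% CI −1.7 to +18.8.

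Both intervals include zero. The upper bound is 13 points for assignment and 19 for treatment received.

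**The case against.** A reader might infer that crossover can hide a harm and that 2.9 then withholds the analysis that would recover it. That does not follow. The IV test is the ITT test rescaled, so an unconditional IV analysis would be non-significant in the same trials. The miss rates implied by the table for r = 0.9 to 0.7 (19% to 65%) are type II error of the ITT test. They would be the same after the fix, and they are already 12% to 38% at full compliance, so much of the loss is sample size rather than dilution.

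Nor does the SAP say that a null ITT test shows no effect of the drug. It only limits a supplementary analysis.

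Other points against also have weight:
- The trial compares management strategies, and clinician-chosen blockade in controls is part of the control strategy. ITT answers that question, is planned for every secondary outcome and is unaffected.
- Any ITT estimate picked out for significance carries the same factor. The difference is that all ITT results will be reported, whereas the IV results would exist only in selected form.
- A reader could approximate the IV estimate for a binary outcome from the ITT difference and the receipt data. That is a reason to report it properly rather than leave it to readers.
- IV validity is open to question. Assignment also sets sedation depth (Protocol 5.1.2 and 5.2.2). Strength testing and the recall questionnaire are attempted only in awake, comprehending patients (Protocol 6.3.2), and long-term measures need survival (SAP 2.8).

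The last point rules out extending IV to every endpoint without qualification. It does not justify choosing by p-value, and the sedation limit applies equally to the primary endpoint, where IV is already planned.

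**Conclusion.** The concern holds, in limited form. Under SAP 2.9, IV estimates for secondary endpoints are selected on significance and exaggerated on average: about 1.1 to 1.7 times the truth under the assumed +10-point harm, 30-40% base rate, 250-450 assessed per arm and receipt difference of 0.9 to 0.7. The factor is near 1 for well-powered outcomes and larger for weakly powered ones. It is an average over trials, not a correction to apply to one result.

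When ITT is null, the loss is an unselected estimate and its wider interval (upper bound 19 rather than 13 points in the example), not a missed significant finding. The primary result and all ITT comparisons stand as planned. Event rates, numbers assessable and receipt rates are assumptions; the direction of both effects does not depend on them, but their size does.

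**What to change.** In SAP 2.9, drop the significance condition. Suggested text: *Whatever the result of the ITT comparison, the effect of treatment received will be estimated by instrumental variables and reported with its 95% confidence interval for the primary endpoint and for the following endpoints: ICU-acquired weakness, paralysis recall, supraventricular tachycardia or new atrial fibrillation, and [others named in advance]. ITT remains the principal analysis.*

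Three additions are needed:
- Define the treatment received, including how partial infusions and control-arm boluses count. Doses in both arms are already collected.
- Name the endpoints explicitly, so that the secondary and safety labels in SAP 1.5 and Appendix A1 no longer decide what is covered.
- Label IV results for outcomes seen only in survivors or awake patients as supplementary, and state that selection and the accompanying sedation difference as limits.

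The cost is a short SAP revision and some supplementary table rows, with no new data. Some estimates will be imprecise, and all rest on IV assumptions.

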### 2.10 Heterogeneity of Treatment Effects

We will use a model fit on the ARMA 6ml/kg data and previously published [5] to develop a risk score for each patient in the study. The variables used were age, APACHE, pplat, missing pplat, number of organ failures, hospital days prior to enrollment, and AADO2. Then as a statistical test we will fit a logistic model with terms for treatment, risk score and a treatment risk score interaction. The significance of the interaction term will test for Heterogeneity of Treatment Effects. In addition as a graphical display of the data we will divide the patients into 10 equal sized group by risk score and plot the mortality difference as a function of risk score group.

## Appendix:

### Appendix A1: Outcome Variables

Variable	Category	Scale	Method
All-cause mortality prior to discharge home before day 90	Primary Outcome	Binary	Wald-test from 90 day KM estimate
ICU acquired weakness	Secondary Outcome	Binary	Monte Carlo Fisher's Exact Test
IL-6 levels (plasma)	Secondary Outcome	Continuous	T-test
Hospital mortality to day 28	Secondary Outcome	Binary	Chi-square Test
Ventilator free days to day 28	Secondary Outcome	Continuous	T-test
Organ failure free days to day 28	Secondary Outcome	Continuous	T-test
ICU-free days at day 28	Secondary Outcome	Continuous	T-test
Hospital-free days at day 28	Secondary Outcome	Continuous	T-test
Oxygenation Index on study days 1-4,7 PaO 2 / FiO 2 ratio on study days 1-4, 7 Level of PEEP on study days 1-4, 7 Plateau pressure on study day 1-4, 7 Development of pneumothorax through day 7	Physiologic measure	Continuous Continuous Continuous Continuous Binary	T-test T-test T-test T-test Fisher's Exact Test
Disability: using Katz Activities of Daily Living (ADL)/Lawton Instrumental Activities of Daily Living Scale (IADL)	Long term outcome assessments	Binary	Chi-square Test

plus two additional Nagi items			
Health-Related Quality of Life (including utilities): EuroQol (EQ-5D-5L)		Continuous	T-test
Self-rated health: 1 standard item		Continuous	T-test
Pain-interference: 1 standard item		Continuous	T-test
Post-traumatic Stress-like Symptoms: Post-Traumatic Stress Symptoms (PTSS-14)		Binary (Part B Score $\geq 45$ )	Chi-square Test
Cognitive function: Montreal Cognitive Assessment (MoCA-Blind)		Continuous Binary ( $< 26$ )	T-test Chi-square Test
Via proxy, the Alzheimer's Disease 8 (AD8)		Continuous	T-test
Subsequent return to work, hospital and ED use, and location of residence		Categorical	Fisher's Exact Test
Use of rescue procedures	Safety	Binary	Fisher's Exact Test

Paralysis recall, in-hospital	Safety	Binary	Fisher's Exact Test
Supraventricular tachycardia (SVT) or new onset atrial fibrillation	Safety	Binary	Fisher's Exact Test

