## 2.8 Long Term Follow Up Data

Six month and one year survival, for each treatment group, will be calculated using a multistate model. Patients will be classified in terms of the following states, 1-Study Hospital, 2-Other Hospital, 3-Home 4-Dead, with possible transitions of 1-2, 1-3, 1-4, 2-3, 2-4. The time duration of each transition that is known will be calculated. Then this model will be used to estimate the 6 and 12 month survival, and its standard error for each treatment group separately[3]. The test of a treatment effect will then be the difference in the survival estimates divided by the pooled standard error. The method of estimation is based on the multiplication of probabilities. For instance, suppose a patient went home at 100 days but only has 120 follow up at the time of analysis or is lost to follow up at 120 days. Then the probability of death for this patient is probability of a transition from 3 to 4, for a patient who has been home for 20 days.

The primary analysis of continuous and ordinal follow up data on patient's functional status will be a comparison of the distribution of these data using the methods described in the analysis methods section 2.3. The primary issue with this choice of analysis is that the treatment difference is difficult to interpret if there is a mortality difference. In that case we will conduct several sensitivity analyses described below.

The problem is that we are measuring follow up variables, for instance the Euro QOL, denoted here as QOL, in some patients on the better treatment who would have died on the worse treatment. When there is a survival difference the simple comparison does not measure the potential harm or benefit of the intervention on QOL. What we seek to estimate, is the *survival average causal effect*, defined as the difference in QOL among patients who would have survived both treatments. We will assume that patients who would survive on the worse treatment will also survive on the better one. In that case, the mean value of QOL on the worse treatment among patients who would have survived on both treatments is just the ordinary mean of QOL on that treatment.

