## Appendix A2: Reference Measurements

Variable	Category	Scale	Method
Time and dose of loading dose		Continuous	Descriptive
Time of initiation of cisatracurium infusion		Continuous	Descriptive
Reason and duration of infusion hold during first 48 hours		Binary>=48.5 hours Continuous	Descriptive
Total dose of cisatracurium infusion during first 96 hours		Continuous	Descriptive
Name and total dose of other NMB during first 96 hours		Dose, Continuous	Descriptive
Additional NMB administered after 96 hours (yes/no)		Binary	Descriptive
Name and total dose of any NMB used in the first 96 hours after randomization (Control Arm)		Binary (Yes/ No) Continuous (Total Dose)	Descriptive
Additional NMB administered after 96 hours (yes/no) (Control Arm)		Binary (Yes/ No) Continuous (Total Dose)	Descriptive

If receiving positive pressure ventilation: Ventilator mode		Categorical, Days 1-4 & 7	Monte Carlo Fisher's Exact Test
If receiving positive pressure ventilation: set rate actual rate minute ventilation tidal volume FiO 2 PEEP I:E ratio, plateau, peak, mean airway pressures set peak flow, set inspiratory time		Continuous, Days 1-4 & 7	T-Test
PaO 2 , PaCO 2 , pH, and SpO 2		Continuous, Days 1-4 & 7	T-Test
Serum electrolytes and glucose		Continuous, Days 1-4 & 7	T-Test
Intravenous sedatives Intravenous opioids Enteral or intravenous corticosteroids		Binary, Days 1-4 & 7	Chi-Square Test
Sedation score: If RASS < -1 (or Riker < 3, Ramsay > 3), and sedation given, list reason given		Reasons (Categorical) Scale Used (Categorical) Light/ Deep/ Agitation (Categorical) Mean score (Continuous)	Chi-square Test Chi-square Test Chi-square Test T-test
Was a sedation interruption performed? Y/N		Binary Daily	Chi-square Test

Fluid intake and output/CVP if available		Continuous	T-Test
ICU Mobility Scale	Safety	Binary (Able to sit at edge of bed or greater)	Fisher's Exact Test
Manual Muscle Testing	Safety	Continuous	T-test

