### Long Term Outcomes

#### Disability: using Katz Activities of Daily Living (ADL)/Lawton Instrumental Activities of Daily Living Scale (IADL) plus two additional Nagi items

ADL/IADL assessments are administered at baseline, months 3, 6 and 12. 2 additional NAGI items were collected at months 3, 6, and 12. The total score is a summation of the all the times. Possible 8 maximum points at baseline and 10 maximum points at follow up. Any missing items are allotted 0 points.

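### SAP A1 tests disability as a binary outcome but no cut-off is defined anywhere, so the listed test cannot be run on the score that A3 derives

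*SAP*

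**What the plan says.** - **SAP Appendix A1** lists "Disability: using Katz Activities of Daily Living (ADL)/Lawton Instrumental Activities of Daily Living Scale (IADL" plus two Nagi items, scale Binary, method chi-square. Neither the row nor its continuation line gives a threshold.
- **SAP Appendix A3** derives a sum: "The total score is a summation of the all the times". Its range is described as "Possible 8 maximum points at baseline and 10 maximum points at follow up", and "Any missing items are allotted 0 points". It does not say whether a high score is good or bad, and it defines no dichotomy.
- **Protocol 3.9.2 and 6.4** name the instrument and the 3, 6 and 12 month interviews but give no threshold. Section 6.4 adds that three ADL/IADL items are dropped in favour of EQ-5D items and that two Nagi items are added.
- **SAP 2.8** states: "The primary analysis of continuous and ordinal follow up data on patient's functional status will be a comparison of the distribution of these data". It refers to section 2.3 for the tests, which for ordinal outcomes means the Cochran-Mantel-Haenszel row-mean-score test.
- **Other dichotomised scales state their rule.** PTSS-14 is cut at a Part B score of 45 or more, MoCA-Blind at below 26, and ICU-acquired weakness at an MRC score below 48. The ICU Mobility Scale is given as "Binary (Able to sit at edge of bed or greater".

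**The concern.** A chi-square test on a two-level outcome needs a rule that assigns each patient to a level. For disability there is none. The variable A3 produces has up to eleven levels at follow-up, so someone must still decide where to split it. The item set is specific to this trial, so no default cut-off follows from the instrument's name, and the unstated scoring direction leaves even the sense of a cut open.

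Two things are at stake. First, an undefined threshold is a free choice in an open-label trial whose secondary outcomes are each tested at two-sided 0.05 without multiplicity correction. Second, splitting a graded score usually discards information, and how much depends on where the split falls.

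**Working it through.** **1. What the plan gives.** No sample size, effect, standard deviation or distribution is stated for disability, so there is no plan figure to reproduce for it. The trial size does reproduce: for 35% v 27%, two-sided 0.05 and power 0.90, n per arm = [1.96√(2×0.31×0.69) + 1.2816√(0.35×0.65 + 0.27×0.73)]² / 0.08² = 701, or 1402 in total, against the stated 1408. It is used here only to anchor the number assessed: 704 × 0.65 ≈ 458 control survivors at the planning rate, or 366 if 80% respond. The response rate is an assumption. The power comparison uses 400 per arm, also an assumption.

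**2. Is there a cut-off anywhere?** SAP A1, A2, A3, 2.3 and 2.8 and protocol 3.9.2, 6.4 and Appendix G contain none for disability. The four comparator scales above all have one, so the gap is specific to this outcome.

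**3. Power, ordinal test v one cut, common odds ratio.** With N = 800 in total and log 1.45 = 0.3716, power ≈ Φ(0.3716√V − 1.96), where p̄ denotes proportions averaged over the arms.
- Single cut: V = (N/4) p̄(1 − p̄). This is largest at p̄ = 0.5: V = 50, 0.3716 × 7.071 − 1.96 = 0.667, power 75%.
- Ordinal rank test: V = (N/12)(1 − Σp̄³). Its ceiling is V = 66.7: 0.3716 × 8.165 − 1.96 = 1.074, power 86%.
- With two categories 1 − Σp̄³ = 3p̄(1 − p̄), so the two formulas agree. Splitting a category lowers Σp̄³. Under a common odds ratio the ordinal test therefore never carries less information than a cut of the same score.

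Worked example: assume control probabilities (11 − k)/66 for k = 0 to 10 (beta-binomial with parameters 1 and 2, mean 3.33).

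| Analysis | Control → treated | V | Power |
|---|---|---|---|
| Ordinal, Σp̄³ ≈ 1/66 | whole score | 65.7 | 85% |
| Cut at ≥3 | 0.545 → 0.453 | 50.0 | 75% |
| Cut at ≥1 | 0.833 → 0.775 | 31.5 | 55% |
| Cut at ≥8 | 0.091 → 0.065 | 14.3 | 29% |

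Simulation over six assumed beta-binomial shapes gave 74-86% for the rank-based ordinal test and 71-76% for the best fixed cut. Ordinal power falls towards the low end when most patients share one score, because Σp̄³ is then large.

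**4. A pattern where a cut wins.** Take the same control distribution with 366 per arm, and let treatment lower the share with any disability by 8 points, from 0.833 to 0.753, leaving the spread among the disabled unchanged. The ≥1 cut has (0.08 − 1.96 × 0.0299)/0.0298 = 0.72, or 76% power. A t-test on the score has 36%. In the most zero-heavy shapes of step 3, a ≥1 cut also beat the t-test, though not the rank-based test.

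**5. Exposure if the cut followed the data.** 20,000 simulated null trials, 366 per arm, three beta-binomial shapes:

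| Parameters | One cut fixed at ≥3 | Best of ≥1, ≥3, ≥5 | Best of ten cuts |
|---|---|---|---|
| 0.4, 0.8 | 5.0% | 11.3% | 23.3% |
| 1, 2 | 4.9% | 12.4% | 27.6% |
| 2, 2 | 5.2% | 13.2% | 29.6% |

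The six-shape simulation with 400 per arm gave 10-14% and 21-29%.

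**The case against.** The strongest reply is that only one number is missing. A sum score in A3 with a binary analysis in A1 is normal in this SAP: PTSS-14 is handled that way and is perfectly clear. SAP 2.8 speaks only of continuous and ordinal follow-up data, so a variable labelled Binary falls under the categorical rule of 2.3. This stands. A reader might infer that A1, A3 and 2.8 contradict one another about which analysis is done, but they can be read consistently once a threshold is supplied.

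A reader might also infer that every threshold is weaker than the score. Step 4 shows this is not general: the ranking depends on where the effect falls, and a plain t-test can lose to a ≥1 cut when many patients score zero.

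Nor do the documents say that the cut will be taken from the data. They are silent, and the figures in step 5 apply only if several cuts were tried and the smallest p-value kept. Binary might also have been meant as any versus none, or as item by item, but the SAP says neither.

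Finally, secondary outcomes carry no multiplicity control in any case, and being listed first among the long-term measures confers no priority. Both are fair limits on importance. They do not supply the missing rule.

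**Conclusion.** The point holds as a gap in specification. The disability test in A1 cannot be applied to the A3 variable, and no passage fills the gap. It goes beyond a missing detail because SAP 2.3 already contains a method that needs no threshold and that, for an effect spread across the scale, would usually be more powerful: about 74-86% against 71-76% for the best cut, and as low as 29% for a poor one in the worked example. These figures rest on assumed distributions, 400 per arm and a common odds ratio of 1.45, none of which is in the documents. An effect confined to any versus no disability could reverse the ranking.

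The open threshold exposes the test to a type I error of about 10-14% over three cuts and 21-30% over ten, against 5% for a fixed one. That measures the freedom left open and does not predict how it will be used. One of seven long-term measures within the secondary outcomes is affected. The primary analysis is not.

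**What to change.** Before unblinded follow-up data are seen:

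1. In A1, change the disability row to the follow-up score, analysed with the row-mean-score test of SAP 2.3. Specify rank scores, since the score may be skewed with many zeros.
2. In A3, state the scoring direction. This also shows which way the rule of scoring missing items as 0 pushes a patient.
3. If a proportion is wanted for reporting, keep a binary version as supportive, with its cut-off fixed in advance in A1 and A3.

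If the sponsor prefers to keep the binary analysis as the main one, fixing the cut-off and direction now would close the specification gap but not the likely power loss. The recommended change costs one table row and a sentence in A3, and gives a result slightly less simple to report than a difference in proportions.
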